## **PROTOCOL AND PROPOSED STATISTICAL ANALYSIS:**

This study will test the effects of an intervention (MAPSS-MS) to promote the cognitive functioning of persons with MS. The effectiveness of the intervention will be examined using a prospective, longitudinal, randomized pretest/posttest usual care comparison group design. The intervention consists of an efficacy-building group intervention that will incorporate an individualized computer-based practice component (CACR) to help participants build self-efficacy for skills to improve cognitive functioning and activities of daily living. The group component of the intervention will provide information specific to cognitive difficulties experienced with MS, help participants assess their difficulties and identify strategies to manage cognitive difficulties and improve performance. The group exercises will focus on helping persons translate the skills they are practicing in the CACR component into everyday life to improve overall functioning and health.

Participants will be recruited from three metropolitan communities in Texas: Houston, San Antonio and Dallas/Fort Worth. The Houston metro area has a population of over 5.9 million persons. The population is approximately 26% white/non-Hispanic, 44% Hispanic, 24% Black, and 6% Asian. The San Antonio metro area has a population of 2.2 million persons; 63% are Hispanic and 7% are African American. More than 6.3 million people live in the Dallas/Fort Worth metroplex; 13% are African-American, 4% Asian or Pacific Islander and 21% are Hispanic or Latino of any race. The Lone Star Chapter of the National MS Society has active offices in each community to support recruitment and implementation.

PI [name] and Co-I [name] have worked with staff of the Lone Star Chapter of the National MS Society for over 20 years and are well known by MS clinicians throughout the state. The research team has substantial experience with conducting multi-site interventions and data collection (RO1HD035047, R21 NR011076; RO1 NR03195) with persons with MS. Use of the three communities will assure the ability to recruit sufficient participants and support the diversity of the sample (MS predominates in women and whites). Neurologists who are MS Specialists in each community have agreed to assist with recruitment (see letters of support) and serve as consultants for patient referral. The Lone Star Chapter of the National MS Society serves more than 21,000 persons with MS in 174 counties in Texas including these communities.

**SAMPLE:** The sample for this study will consist of persons with physician-diagnosed MS living in the identified Texas metropolitan areas who are concerned about their cognitive problems.

**SAMPLE SIZE:** Power analyses were conducted using data from our recent preliminary study. The initial sample size estimate was based upon an  $f$  value of .38 for the interaction of time by group for the CVLT-Total. The alpha level was set at .01 to account for the multiple analyses that

are proposed to answer the research questions. A minimum sample of 80 was estimated to have 80% power to detect a statistically significant time x experimental group interaction with a .38 effect size. However, we propose to power the study based upon a lower f value of .28, which corresponds more closely to the effect sizes observed for the other neuropsychological tests. Therefore, 180 individuals will be needed to detect an effect size (f) of .28 as statistically significant. This larger sample size will also provide sufficient power for the more complex 3 site nested design. Based on our preliminary study we estimate that 20% of potential participants who respond to recruitment materials will not meet the inclusion criteria and an additional 25-30% will be unable to attend the classes when scheduled. Thus, we will need to screen 320 persons to recruit a sample of 180 participants (60 at each site). Given the number of participants who consent and do not complete the full data collection we will need to recruit up to 230 persons with MS. The number of persons with MS in the 3 communities is more than sufficient.

**INCLUSION/EXCLUSION CRITERIA:** To participate, subjects must be diagnosed with MS, age 18 to 60, and capable of understanding and complying with the study protocol. Participants must be able to read and write in English and have visual acuity of at least 20/70 with correction in order to work on the computer screen. All participants must have a clinically definite diagnosis of MS that is documented by their physician. Participants must have stable disease at the time of entry into the study (relapse free for at least 90 days), have subjective concerns about their cognitive functioning (based on the Perceived Deficits Questionnaire), have home internet access, and be willing to participate in an 5 month study involving education/skill building, support and data collection. Participants may be of either gender or any ethnic/racial group. Subjects will be excluded if they have other medical causes of dementia or other neurological disorders that may impact cognition or emotions, evidence of major psychiatric disorder or if they have major functional limitations that preclude them from participating in the study.

**RECRUITMENT AND SCREENING:** Participants will be recruited in a variety of ways including fliers in offices of physicians, targeted mailings to persons with MS on the mailing list of the National MS Society, contact with support groups, notices in MS newsletters and “word of mouth.” Letters of support for recruitment are appended. Recruitment materials will instruct potential participants to call the research office 800 number for additional information about the study. The project staff will have a script to screen potential participants for inclusion/exclusion criteria and will explain the study procedures and requirements to those who are eligible. The Perceived Deficits Questionnaire (Sullivan, Edgley & Dehoux, 1990) will be administered by phone and those scoring indicating they experience at least 5 problems “sometimes” or more often will be eligible to participate. Participants will be asked to provide the name and address of their physician, who will be asked to verify the diagnosis and give a medical clearance for the individual to participate. Recruitment will be ongoing in order to establish a pool of potential participants at each of the three sites. Nine cohorts of 20-22 subjects will be randomly selected (three times at each of three sites) during the study and subjects within the cohort will be randomly assigned (following baseline testing) to the treatment or comparison group. In prior studies, small intervention class sizes (n=10-12) enhanced self-efficacy through vicarious experience and modeling.

Persons who do not qualify to participate in the study based on the screening criteria will be thanked for their interest and receive a brochure from the MS Society on cognitive strategies.

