**Data Analysis:** Inferential analysis will be used to test the study hypotheses. Data analyses will be conducted using SPSS.. Neuropsychological data will be scored by the testers and verified by a second staff member. Data will be entered and checked for accuracy. Internal consistency reliability coefficients for all self-report measures will be assessed with an expectation of alpha = .80 or above. Descriptive analyses will be used to obtain a profile of the sample. The groups will be compared at baseline on demographic and disease variables. Preliminary analysis for tests of assumptions such as normality, independence of errors, homogeneity of variance, and outliers will be conducted to determine if data transformations are necessary.

Missing data are often problematic for randomized controlled trials and various strategies are often used to manage missing data. We will use intention-to-treat strategies to handle missing data. More specifically, a “last observation carried forward” (LOCF) strategy in which missing data points are imputed based on the participant’s existing data.

To account for cohort and city effects, multi-level analyses using SAS Proc Mixed will be conducted and any major effects observed will be included in subsequent analyses. A repeated measures (RM-ANOVA) design will be used to determine time and time by group effects on performance and self-report outcomes. Because of the large variability expected in a community-residing sample of persons with MS, we will use Analysis of Covariance (ANCOVA) to control for the differences among participants that are not germane to assessing the magnitude of the difference attributable to the treatment. Therefore, ANCOVAs will be performed to determine the differences between the intervention group and comparison groups at T2, T3, and T4, after controlling for baseline scores. Separate analyses will be conducted for each outcome measure.

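### N=80 at f=.38 and N=180 at f=.28 cannot come from one calculation, and the nested-design power claim has no ICC or design effect behind it

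*Combined protocol and SAP*

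**What the plan says.** All of the derivation is in the Sample Size paragraph of the combined protocol and SAP. It sets alpha at .01 for multiplicity and takes f=.38 for CVLT-Total from the preliminary study: "A minimum sample of 80 was estimated to have 80% power to detect a statistically significant time x experimental group interaction". It then changes the effect size, "However, we propose to power the study based upon a lower f value of .28", and concludes "Therefore, 180 individuals will be needed to detect an effect size (f) of .28 as statistically significant". The sentence giving 180 does not restate power, alpha, degrees of freedom or test.

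The next sentence adds: "This larger sample size will also provide sufficient power for the more complex 3 site nested design". No ICC, cluster size or design effect is given there or elsewhere. Attrition comes afterwards: "Given the number of participants who consent and do not complete the full data collection we will need to recruit up to 230 persons".

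Recruitment and Screening describes nine cohorts of 20 to 22, three per site, randomised within cohort, with intervention classes of about 10 to 12. Data Analysis says "A repeated measures (RM-ANOVA) design will be used to determine time and time by group effects", followed by ANCOVAs at T2, T3 and T4 adjusted for baseline. For clustering it says "To account for cohort and city effects, multi-level analyses using SAS Proc Mixed will be conducted".

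**The concern.** As the paragraph reads, only f changes between the two sample sizes, and 180 is presented as following from that change. Required N then scales almost exactly as 1/f², and 180 is too far above 80 for that. At least one figure is therefore wrong as written, or the two rest on different unstated tests or power levels.

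This is the plan's only sample-size derivation. The 60 per site, the 320 screened and the 230 recruited all rest on 180. The nested-design assurance depends on the same answer: whether 180 holds any reserve for participants sharing a class cannot be judged until it is known what 180 gives for independent participants.

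**Working it through.** **Inputs.** From Sample Size: alpha .01; 80% power (stated for N=80 only); f=.38 with N=80; f=.28 with N=180. From Data Analysis: baseline, T2, T3 and T4, so a four-occasion interaction between two groups has 3 df. Assumed: 80% power carries over to 180. Not stated: the occasions and df in the power calculation, the definition of f, and the within-person correlation.

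**1. Can the plan's figures be reproduced?** I used a noncentral F test with noncentrality λ = N·f², alpha .01, df1 = 1, 2 or 3, and df2 = N−2 or (N−2)·df1. Where the two choices of df2 differ, a range is shown.

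| df1 | N for 80% at f=.38 | N for 80% at f=.28 | Power of 80 at f=.38 | Power of 180 at f=.28 |
|---|---|---|---|---|
| 1 | 85 | 153 | 77% | 87% |
| 2 | 99–101 | 180–182 | 66–68% | 80% |
| 3 | 109–113 | 200–203 | 58–61% | 73–74% |

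The figure of 180 is reproduced by a 2-df interaction, such as two groups by three occasions. The figure of 80 is approached only by a 1-df test (85 here; 82 by the normal approximation, which gives 150 at f=.28). No row gives both. If λ is also multiplied by the number of occasions minus one, the pairs are 51 and 91 (three occasions) or 38 and 68 (four), which match neither figure.

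**2. The ratio, which does not depend on the convention.**
- Stated: 180/80 = 2.25.
- Pure scaling: (.38/.28)² = 1.842.
- From the variants above: 153/85 = 1.80, 182/101 = 1.80, 203/113 = 1.80, 91/51 = 1.78, 68/38 = 1.79.
- Rounding limit, with .38 taken as .385 and .28 as .275: (.385/.275)² = 1.96, so 80 × 1.96 = 157.

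**3. Each figure taken as correct in turn.** Set λ = c·f²·N and choose c so that the anchor has exactly 80% power. The constant c absorbs the definition of f and the within-person correlation.
- Anchor N=80 at f=.38: f=.28 needs 142.6 to 145.7 over 1 to 3 df, or 80 × 1.842 = 147.3 by scaling, so about 143 to 147. On this anchor 180 has 89 to 91% power.
- Anchor N=180 at f=.28: f=.38 needs 98.6 to 100.3, or 180/1.842 = 97.7 by scaling, so about 98 to 101. On this anchor 80 has 66 to 68% power.

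**4. What this leaves for nesting.**
- If 80 is right, 180 exceeds the need by 180/147.3 = 1.22 to 180/142.6 = 1.26, a reserve of 22 to 26%.
- If 180 is the 80%-power N for independent participants, the reserve is zero.
- If the test is the 3-df interaction with λ = N·f², 180 is 20 to 23 short before any clustering.

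The plan does not say which case applies and gives no ICC to set against it.

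**The case against.** The strongest reply is that 80 is only an initial estimate that the plan replaces and never uses, so 180 may be sound. That stands: a 2-df interaction with λ = N·f² gives 180 almost exactly. A reader might infer that the right answer is 143 to 147 and that 33 to 37 participants are unexplained. That follows only if 80 is correct, which the documents do not establish.

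The opposite inference, that the trial is underpowered because four occasions give 3 df and 73 to 74% power, is not established either. It needs λ = N·f² and a power calculation based on all four occasions. Under another definition of f, or on the N=80 anchor, 180 is more than enough.

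It is also fair to say that the two figures could come from calculations with different df or power. About 90% power, f near .25, rounding to nine cohorts of 20, or a clustering allowance would each bring 80 into line with 180. None is stated, so this moves the fault from arithmetic to reporting without removing it.

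Dropout is a weaker explanation but cannot be excluded. The 230 sentence suggests that losses are added on top of 180. Yet 320 are screened to recruit 180, and nine cohorts of 20 to 22 hold only 180 to 198, not 230. If 180 means enrolled, an assumed 20% loss gives 144/0.80 = 180.

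On nesting, randomisation within cohort and the planned multi-level model deal with part of the cohort and city effects. Clustering by class remains, because intervention participants share a group while comparison participants receive only telephone calls. That makes the assurance unsupported; it does not make it false.

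**Conclusion.** The concern holds as an internal inconsistency. With one test, alpha .01 and one power level, 80 at f=.38 and 180 at f=.28 cannot both stand: the ratio is 2.25 against about 1.8, with a ceiling of 1.96. This does not depend on the definition of f or the within-person correlation, since both cancel in the ratio. It does assume that test, alpha and power are the same for both figures, as the text implies but does not state.

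Which figure is wrong, and so whether 180 carries a surplus, an exact fit or a shortfall, is not determined. Taken directly with λ = N·f², power at 180 is 87%, 80% or 73 to 74% for 1, 2 or 3 df. The nested-design sentence has no ICC or design effect behind it, and on the reading that best reproduces 180 there is no reserve for class clustering. The documents show neither that 180 is too small nor that it is sufficient.

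**What to change.** Run the calculation once, for one named test, and replace the two sample-size sentences with the result:
- State the test, numerator df, number of occasions, definition of f, assumed within-person correlation and alpha .01.
- Report the N for 80% power at f=.28, and the power that 180 analysed participants give before clustering.
- Correct 80 from the same run, or delete it. As a check, if 80 is confirmed at 80% power, the N at f=.28 should be about 143 to 147. If 180 is confirmed, 80 should become about 98 to 101.
- Say whether 180 means enrolled or completing, and reconcile it with the 230 recruited and the nine cohorts of 20 to 22.
- Replace the nested-design sentence with the power at 180 over a stated range of assumed class ICCs, naming the method and error df.

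Keep N at 180, and restate the power if it proves lower. The cost is one re-run and a few sentences. The downside is that the stated power, especially under nesting, may look less favourable than the present wording.

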## INTERVENTION: MAPSS - MS

The overall purpose of the MAPSS-MS intervention is to help the individual acquire the highest level of cognitive functioning and functional independence. This is accomplished through teaching the use of compensatory skills, retraining skills (the CACR component) and environmental/lifestyle support for cognitive functioning. The MAPSS-MS has two components: (a) Group sessions focused on building efficacy for use of cognitive strategies and (b) an innovative computer assisted cognitive rehabilitation (CACR) program. The home-based computer component will enable the participants to engage in intensive practice sessions without leaving their homes. Translation of skills practiced to everyday issues will be a focus of the group sessions.

Group Component The investigators' prior work will drive the content and process aspects of the MAPSS-MS (Memory, Attention & Problem Solving Skills for Persons with MS) intervention - specifically the health promotion intervention for women with MS (R01HD35047). The intent of the efficacy-based wellness intervention is to engage individuals in assessing their present health behaviors, setting meaningful goals for change and addressing the barriers, resources and skills necessary to improve health behaviors and consequently quality of life. In this study, we will use the same process and strategies ([name], et al., 1999; [name] et al., 2003) to assist participants to acquire knowledge regarding the specific MS-related cognitive impairments; assess and acknowledge their cognitive concerns, build the skills necessary to implement compensatory self-management strategies of cognitive difficulties and set goals for integrating new cognitive skills into their everyday lives.

The group program will consist of weekly 2-hour classes over an 8 week period that present information, guide participants in self-assessment of cognitive problems, resources and barriers to cognitive functioning and enhancing self-efficacy for use of strategies to maximize cognitive functioning. Four major topic areas will be included in the lifestyle change classes (1) Identifying common cognitive problems experienced with MS (2) Compensatory Strategies to Maximize cognitive Skills (3) Maximizing Cognitive Health with a MS – Lifestyle adjustments (e.g. physical activity and energy conservation) to promote cognitive functioning (3) Adjusting to Changes in Cognitive Skills (4) Stress Management (controlling anxiety) and Enhancing Cognition. At each session, the facilitator will evaluate the participants on CACR exercises prescribed at the last session, troubleshoot cognitive strategies and performance difficulties, and prescribe the therapy exercise assignments for the upcoming week.

Computer Assisted Cognitive Rehabilitation (CACR) protocol: In response to the feedback obtained in preliminary studies, we will use the computer training exercises from Lumosity. The computer protocol for this multi-site trial follows:

Computer Protocol: The computer training methodology developed by Lumos Labs, Inc. (San Francisco, CA) uses an open-innovation model targeting effectiveness, designed to adapt to the individual user, offering novel and engaging tasks and challenges within a integrated, hierarchical structure. The Lumosity program has been used in research with childhood cancer

survivors, healthy adults, and older persons with mild cognitive impairment. The Lumosity website ([www.lumosity.com](http://www.lumosity.com)) delivers interactive programs and applications that run directly in standard web browsers. Users need only a computer, tablet, or smart phone to access the website and securely log into the program. The PIs will contract with Lumos Labs, (see letter of support) for use of the Lumosity program including development of a suite of specific games/training activities and the collection and delivery of data collected on all participants enrolled in the study. Research staff will register each participant on the Lumosity website using anonymous user ID numbers and passwords allowing participants unlimited access throughout the 8-week intervention period. The delivery of the computer exercises over the Internet allows the participant to complete the exercises from any location on any device with Internet access at any time. During the first group session the facilitator will demonstrate logging on and navigating the website before having the participants practice these skills and work through sample exercises using laptops connected to the internet. As each participant works through a session, the data is saved on the website's servers and the participant is able to start subsequent sessions where he/she stopped progressing in hierarchical fashion. Each participant will be asked to complete a minimum of 45 minutes of training three times per week and to keep a written log of practice times and dates. The researchers will monitor the skills practiced and the success at various levels via data reports provided via e-mail by Lumos, Labs.

The facilitator will prescribe 2 consecutive weeks of practice with 4 of the Lumosity boost programs addressing the most common problems experienced by persons with MS. The tasks are arranged so that the most basic cognitive skills (attention) are addressed first. As the user progresses, the tasks become more challenging. Each boost is set up in a game like format. The facilitator will be available to participants by phone and email and will contact each participant weekly by phone to assess for any problems using the program.

*Weeks 1 & 2 Attention Boost:* provides training targeting visual field and focusing. Exercises include: *Lost in Migration*, a selective attention task based on the flanker test paradigm, and *Bird Watching*.

*Weeks 3 & 4 Memory Boost:* provides training on skills essential to store, retain and recall information, events and procedures. Working memory skills are frequently used to accomplish everyday functioning (using a phone) and evidence suggests that working memory can be expanded and enhanced by practice and the use of compensation techniques. Exercises in the memory boost include: *Spatial Speed Match*, which targets working memory and is based on the n-back working memory paradigm, and *Memory Matrix*, which target spatial memory.

*Weeks 5 & 6 Flexibility Boost:* provides training on executive function/flexibility skills that play a major role in information processing, abstract thinking, problem solving, initiation and inhibition. Exercises address task switching, which is trained in the Brain Switching game, response inhibition, planning, and verbal fluency.

*Weeks 7 & 8 Problem Solving Boost:* provides training on problem solving skills to analyze the facts of a situation so that accurate conclusions are made (e.g. calculating a restaurant bill). This boost includes logical reasoning games such as *By the Rules*, based on the Wisconsin Card Sorting Test, arithmetic, and quantitative reasoning.

**Comparison Group:** Persons who are randomly assigned to the usual care comparison group will receive their usual care and a referral to "MyBrainGames", available for free at

MultipleScerosis.com. The games (Shopping List, Word Connect and Round Up) were launched in 2009 by the MS Technology collaborative and challenge the player's processing speed, working memory attention and task switching ability. We will not prescribe any specific amount of practice and participants will be asked to keep a log of any practice time— our preliminary studies have shown that self-report logs are significantly correlated ( $r=.96$ ) to electronic monitoring logs. Participants will receive a weekly phone call to maintain their connection to the study but no other interventions. The comparison group will be asked to complete all data collection on the same schedule as the intervention participants and offered the printed intervention materials after the study.

**Data Analysis:** Inferential analysis will be used to test the study hypotheses. Data analyses will be conducted using SPSS.. Neuropsychological data will be scored by the testers and verified by a second staff member. Data will be entered and checked for accuracy. Internal consistency reliability coefficients for all self-report measures will be assessed with an expectation of alpha = .80 or above. Descriptive analyses will be used to obtain a profile of the sample. The groups will be compared at baseline on demographic and disease variables. Preliminary analysis for tests of assumptions such as normality, independence of errors, homogeneity of variance, and outliers will be conducted to determine if data transformations are necessary.

Missing data are often problematic for randomized controlled trials and various strategies are often used to manage missing data. We will use intention-to-treat strategies to handle missing data. More specifically, a “last observation carried forward” (LOCF) strategy in which missing data points are imputed based on the participant’s existing data.

To account for cohort and city effects, multi-level analyses using SAS Proc Mixed will be conducted and any major effects observed will be included in subsequent analyses. A repeated measures (RM-ANOVA) design will be used to determine time and time by group effects on performance and self-report outcomes. Because of the large variability expected in a community-residing sample of persons with MS, we will use Analysis of Covariance (ANCOVA) to control for the differences among participants that are not germane to assessing the magnitude of the difference attributable to the treatment. Therefore, ANCOVAs will be performed to determine the differences between the intervention group and comparison groups at T2, T3, and T4, after controlling for baseline scores. Separate analyses will be conducted for each outcome measure.

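### LOCF is the only missing-data method planned; it shrinks lasting effects, can overstate fading ones at T3 and T4, and has a cheap replacement

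*Combined protocol and SAP*

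**What the plan says.** The Data Analysis section states "We will use intention-to-treat strategies to handle missing data" and then makes this specific as LOCF: a "LOCF) strategy in which missing data points are imputed based on the" participant's own earlier data. It states no missingness assumption and no sensitivity analysis. The outcome analyses are a repeated-measures ANOVA for time and time-by-group effects, and baseline-adjusted comparisons: "ANCOVAs will be performed to determine the differences between the intervention group and comparison groups at T2, T3, and T4". A mixed model is planned too ("multi-level analyses using SAS Proc Mixed will be conducted"), but to look for cohort and city effects.

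Four other places bear on the point:
- Recruitment and Screening: "Nine cohorts of 20-22 subjects will be randomly selected (three times at each of three sites) during the study", with random assignment after baseline testing.
- Sample Size: 180 participants are needed, and "Given the number of participants who consent and do not complete the full data collection we will need to recruit up to 230". No dropout rate, timing or split by arm is given.
- Inclusion/Exclusion Criteria: participants must "be willing to participate in an 5 month study involving education/skill building, support and data collection".
- Computer Protocol: program access is described as "allowing participants unlimited access throughout the 8-week intervention period".

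**The concern.** Calling LOCF an intention-to-treat strategy keeps everyone in the dataset, but it does not make the carried values right. Because randomisation follows baseline testing, anyone who leaves before T2 is scored as having no change at every later visit. Training access lasts 8 weeks of a 5-month study, so scores may rise, hold or fade after training, and LOCF assumes none of these.

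At stake are the T2, T3 and T4 contrasts and the time-by-group test for every outcome. LOCF is often defended as conservative. If that fails here, a fading benefit could be reported as lasting, and nothing in the plan would show the reader how much depends on the carried values.

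**Working it through.** **Loss after randomisation.** The plan gives no dropout rate to reproduce, so it has to be bounded.
- Randomised: 9 × 20 = 180 (the stated requirement) to 9 × 22 = 198. If 180 must complete, loss is at most 1 − 180/198 = 9.1%.
- Recruited: 1 − 180/230 = 21.7%. Part of this may fall before randomisation, where LOCF does not apply, so it is used only as a stress case.

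**Assumptions, not in the documents.** 1:1 allocation, 99 per arm, correlation .7 between visits, retest gain 0.5 SD, and the effect profiles and dropout patterns below. The largest effect, 0.56 SD, is 2 × the planned f of .28. It is an illustration, not the plan's interaction effect, and no power claim is made.

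**Equal dropout, formula.** LOCF estimate at a visit = sum over last visit seen of (share × effect at that visit), with effect 0 at baseline.
- At T2 only baseline can be carried, so the estimate is (1 − q) × effect, where q is the share with baseline only. This is always towards zero.
- At T3 and T4 earlier effects are carried too, so a fading effect can be overstated.

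**Equal dropout, results at T4.** Early = all leavers go before T2. Spread = last visit equally baseline, T2 or T3. Late = last visit equally T2 or T3.

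| Effect at T2/T3/T4 (SD) | True T4 | 9.1%: early / spread / late | 21.7%: early / spread / late |
|---|---|---|---|
| .56/.56/.56 | .56 | .51 / .54 / .56 | .44 / .52 / .56 |
| .56/.37/.19 | .19 | .17 / .20 / .215 | .15 / .22 / .25 |
| .56/.28/0 | 0 | 0 / .025 / .038 | 0 / .061 / .091 |

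For example:
- Constant effect, early: .909 × .56 = .51 and .783 × .56 = .44, errors of .05 and .12.
- Second row, late, 9.1%: .909 × .19 + .0455 × (.56 + .37) = .215.
- Third row, late: .0455 × .84 = .038 and .1087 × .84 = .091.
- A growing effect (.19/.37/.56) at 9.1%: .51 early; .909 × .56 + .0303 × .56 = .53 spread.

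**Unequal dropout, no true effect.** Bias = −(q1 − q0) × gain, where q1 and q0 are the baseline-only shares in the intervention and comparison arms.
- Loss 12.6% vs 5.6%: −.070 × .5 = −.035 early; a third of that, −.012, spread.
- Loss 30% vs 13.4%: −.166 × .5 = −.083 early; −.028 spread.
- The sign reverses if the comparison arm loses more.

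**Rejection at nominal 1%** (simulation, 40,000 trials per scenario, LOCF with ANCOVA at T4):
- No effect, equal dropout: about 1%, so type I error is held.
- Effect faded to zero, late loss: 1.6% at 9.1% and about 4.4% at 21.7%.
- No effect, unequal early loss: about 1.5% for 12.6% vs 5.6%, and about 4.4% for 30% vs 13.4%.

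**Alternatives.**
- A constrained-baseline mixed model on observed scores was within .001 of the truth in these scenarios, with null rejection of 0.9% to 1.0%.
- The planned ANCOVA on observed T4 scores without LOCF was within about .002 in the runs where dropout did not depend on scores.
- When dropout depended on the last observed score (true .56), LOCF gave .543 to .523 at 9.1% and .516 to .475 at 21.7%. The mixed model gave .559 to .560, and the observed-score ANCOVA .555 to .574.
- When dropout depended on the unseen score in the intervention arm only, with no effect, the mixed model's bias was +.015 at 9.1% and +.039 at 21.7%, against +.006 and +.015 for LOCF.

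**The case against.** The strongest reply is that the harm is small and the remedy large. At 9.1% loss no error exceeds about 0.05 SD, and the worst rejection rate is about 1.6% against 1%. That stands. Even the 9.1% is an inference from cohort size, not a stated attrition allowance.

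It also stands that the simulations favour the mixed model: most remove people independently of their scores, from data that match the fitted model, with no cohort or site clustering. Simply dropping LOCF from the planned ANCOVAs removes most of the bias, so the full model is preferred but is not the only sound choice.

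A reader might infer more than the documents support:
- *That LOCF can inflate every contrast, T2 included.* With equal dropout it cannot at T2. Inflation there needs more loss in the comparison arm and a retest gain.
- *That dropout will differ by arm.* Nothing says so, and both arms get weekly telephone contact.
- *That 21.7% will be lost after randomisation.* The 230 are people recruited, not people randomised.
- *That the effect peaks at T2 and then fades.* The timing of T2 to T4 is not given. If T2 precedes the peak, carrying it forward shrinks the effect.

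None of this rescues LOCF as the sole method. The conservative defence fails at T3 and T4 even with equal dropout.

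**Conclusion.** The point holds as a cheap improvement, not as a threat to the trial's validity. The directions follow from the formula and need few assumptions. The sizes depend on the assumed profiles, retest gain, correlation and dropout patterns: at most about 0.05 SD at T4 with 9.1% loss, and up to about 0.12 SD with 21.7%.

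It would go too far to conclude that LOCF makes false positives likely, or that a mixed model is always less biased. With no effect at any visit and equal dropout, type I error is held. If dropout depends on unseen scores, the mixed model can be the more biased of the two, which is why the sensitivity analysis belongs in the fix.

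**What to change.** 1. Delete LOCF as the primary method. For each outcome, fit one likelihood-based repeated-measures mixed model in Proc Mixed to all observed scores, by randomised group. Include group, visit, group-by-visit, unstructured within-person covariance, and cohort and site terms (stating whether fixed or random). Enter baseline as a repeated outcome with the arm means constrained equal, so that participants with only a baseline score stay in. Take the interaction test and the T2, T3 and T4 contrasts from this model.
2. At a minimum, run the planned baseline-adjusted ANCOVAs on observed scores without LOCF. This drops participants with only a baseline score.
3. State the missing-at-random assumption.
4. Add delta-adjusted multiple imputation with deltas fixed in advance: 0 to 0.5 baseline SD in the unfavourable direction for each outcome, with the sign reversed where higher scores are worse. Apply them in the intervention arm, then the comparison arm, then both, and say whether deltas accumulate over visits. A 0.1 SD delta in one arm moves its T4 contrast by .1 × .091 = .009 or .1 × .217 = .022. The mixed-model bias above is offset at about .015/.091 = .16 to .039/.217 = .18 SD, inside the range.
5. Report dropout by arm and visit.

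Cost: extra SAS programming per outcome and several imputation settings (in steps of 0.1 SD, 1 + 3 × 5 = 16 per outcome), with no new data, participants or staff. The downside is a primary result that rests on missing at random, which the delta analysis probes but cannot prove.
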